8.2.2 Guidelines for Evaluation of Measurable Disease

All measurements should be taken and recorded in metric notation using a ruler or calipers. All baseline evaluations should be performed as closely as possible to the beginning of treatment and never more than 4 weeks before the beginning of the treatment.

The same method of assessment and the same technique should be used to characterize each identified and reported lesion at baseline and during follow-up. Imaging-based evaluation is preferred to evaluation by clinical examination when both methods have been used to assess the antitumor effect of a treatment.

Clinical lesions. Clinical lesions will only be considered measurable when they are superficial and ≥ 10 mm diameter as assessed using calipers (e.g., skin nodules). In the case of skin lesions, documentation by color photography, including a ruler to estimate the size of the lesion, is recommended. When lesions can be evaluated by both clinical exam and imaging, imaging evaluation should be undertaken since it is more objective and may be reviewed at the end of the study.

Chest x-ray. Chest CT is preferred over chest x-ray, particularly when progression is an important endpoint. Lesions on chest x-ray may be considered measurable if they are clearly defined and surrounded by aerated lung.

Conventional CT and MRI. This guideline has defined measurability of lesions on CT scan based on the assumption that CT slice thickness is 5 mm or less. When CT scans have slice thickness > 5 mm, the minimum size for a measurable lesion should be twice the slice thickness. Contrast enhancement should normally be used, unless the patient is allergic. MRI is acceptable in certain situations (e.g., at the Investigator's discretion for CNS metastases, or in cases with iodine contrast allergy).

PET-CT. At present, the low dose or attenuation correction CT portion of a combined PET-CT is not always of optimal diagnostic CT quality for use with RECIST measurements. However, if the site can document that the CT performed as part of a PET-CT is of identical diagnostic quality to a diagnostic CT (with IV and oral contrast), then the CT portion of the PET-CT can be used for RECIST measurements and can be used interchangeably with conventional CT in accurately measuring cancer lesions over time. Note, however, that the PET portion of the CT introduces additional data which may bias an investigator if it is not routinely or serially performed.

Ultrasound (US). US should not be used to measure tumor lesions. US examinations cannot be reproduced in their entirety for independent review at a later date because they are

operator dependent. If new lesions are identified by US, confirmation by CT or MRI is advised. If there is concern about radiation exposure at CT, MRI may be used instead of CT.

Endoscopy, Laparoscopy. The utilization of these techniques for objective tumor evaluation is not advised. However, such techniques can be useful to confirm complete pathological response when biopsies are obtained or to determine relapse in trials where recurrence following CR or surgical resection is an endpoint.

Tumor markers. Tumor markers alone cannot be used to assess objective tumor response. If markers are initially above the upper normal limit, they must normalize for a patient to be considered in complete clinical response.

Cytology, Histology. These techniques can be used to differentiate between PR and CR in rare cases (e.g., residual lesions in tumor types such as germ cell tumors, where known residual benign tumors can remain).

8.2.3 Response Criteria

8.2.3.1 Evaluation of Target Lesions

- Complete Response (CR): Disappearance of all target lesions. Any pathological lymph nodes (whether target or non-target) must have reduction in short axis to < 10 mm.
- Partial Response (PR): At least a 30% decrease in the sum of diameters of target lesions, taking as reference the baseline sum diameters.
- Progressive Disease (PD): At least a 20% increase in the sum of diameters of target lesions, taking as reference the smallest sum on study (this includes the baseline sum if that is the smallest). In addition to the relative increase of 20%, the sum must also demonstrate an absolute increase of at least 5 mm. The appearance of one or more new lesions is also considered progression.
- Stable Disease (SD): Neither sufficient shrinkage to qualify for PR nor sufficient increase to qualify for PD, taking as reference the smallest sum diameters while on study.

8.2.3.1.1 Assessment of Target Lymph Nodes

Lymph nodes identified as target lesions should always have the actual short axis measurement recorded (measured in the same anatomical plane as the baseline exam), even if the nodes regress to below 10 mm on study. In order to qualify for CR, each node

must achieve a short axis < 10 mm. For PR, SD, and PD, the actual short axis measurement of the nodes is to be included in the sum of target lesions.

8.2.3.1.2 Target Lesions that Become “too small to measure”

All lesions (nodal and non-nodal) recorded at baseline should have their actual measurements recorded at each subsequent evaluation, even when very small (e.g., 2 mm). If it is the opinion of the radiologist that the lesion has disappeared, the measurement should be recorded as 0 mm. If the lesion is believed to be present and is faintly seen but too small to measure, a default value of 5 mm should be assigned.

8.2.3.1.3 Lesions that Split or Coalesce on Treatment

When non-nodal lesions fragment, the LD of the fragmented portions should be added together to calculate the target lesion sum. Similarly, as lesions coalesce, a plane between them may be maintained that would aid in obtaining diameter measurements of each individual lesion. If the lesions have truly coalesced such that they are no longer separable, the vector of the LD should be the maximal LD for the ‘coalesced lesion’.

8.2.3.2 Evaluation of Non-target Lesions

Complete Response (CR): Disappearance of all non-target lesions and normalization of tumor marker level. All lymph nodes must be non-pathological in size (< 10 mm short axis).

Non-CR/Non-PD: Persistence of one or more non-target lesion(s) and/or maintenance of tumor marker level above the normal limits.

Progressive Disease (PD): Unequivocal progression of existing non-target lesions. (The appearance of one or more new lesions is also considered progression.) To achieve ‘unequivocal progression’ on the basis of the non-target disease, there must be an overall level of substantial worsening in non-target disease such that, even in the presence of SD or PR in target disease, the overall tumor burden has increased sufficiently to merit discontinuation.

8.2.3.3 New Lesions

The finding of a new lesion should be unequivocal (i.e., not attributed to differences in scanning technique, change in imaging modality, or findings thought to represent something other than tumor, such as a ‘new’ healing bone lesion). A lesion identified on a follow-up study in an anatomical location that was not scanned at baseline is considered a new lesion and will indicate disease progression. If a new lesion is equivocal, continued therapy and

follow-up evaluation will clarify if it represents truly new disease. If repeat scans confirm this is definitely a new lesion, then progression should be declared using the date of the initial scan.

8.2.3.4 Evaluation of Best Overall Response

The best overall response is the best response recorded from the start of the treatment until disease progression/recurrence (taking as reference for PD the smallest measurements recorded since the treatment started). The patient's best overall response assignment will depend on findings of both target and non-target disease and will also take into consideration the appearance of new lesions. Furthermore, depending on the nature of the study, it may also require confirmatory measurement. Specifically, in non-randomized trials where response is the primary endpoint, confirmation of PR or CR is needed to deem either one the "best overall response".

It is assumed that at each protocol-specified time point, a response assessment occurs. [Table 6](#) provides a summary of the overall response status calculation at each time point for patients who have measurable disease at baseline. When patients have non-measurable disease, [Table 7](#) should be used.

Table 6: Time point response: Patients with target (+/- non-target) disease

Target Lesions	Non-target Lesions	New Lesions	Overall Response
CR	CR	No	CR
CR	Non-CR / non-PD	No	PR
CR	Not evaluated	No	PR
PR	Non-PD or not all evaluated	No	PR
SD	Non-PD or not all evaluated	No	SD
Not all evaluated	Non-PD	No	NE
PD	Any	Yes or No	PD
Any	PD	Yes or No	PD
Any	Any	Yes	PD
CR=complete response, PR=partial response, SD=stable disease PD=progressive disease, NE=not evaluable			

Table 7: Time point response: Patients with non-target disease only

Non-target Lesions	New Lesions	Overall Response
CR	No	CR
Non-CR / non-PD	No	Non-CR / non-PD*
Not all evaluated	No	NE
Unequivocal PD	Yes or No	PD
Any	Yes	PD
CR=complete response; PD=progressive disease; NE=not evaluable * Non-CR/non-PD is preferred over SD for non-target disease		

Best response determination for studies where confirmation of CR or PR is required: CR or PR may be claimed only if the criteria for each are confirmed by a repeat assessment at 4 weeks but no more than 5 weeks later for patients in dose levels 1-4 in Part A (0.15 mg/kg, 0.3 mg/kg, 0.6 mg/kg, 1.2 mg/kg), after the criteria for response are first met. Response will be confirmed after 4 weeks or at the next scheduled scan (at Week 6 of the following cycle) for patients in dose level 5 (1.6 mg/kg) in Part A and all patients in Part B. If a confirmative scan is done after 4 weeks, the next scheduled scan (at Week 6 of the following cycle) may be omitted. In this circumstance, the best overall response can be interpreted as in [Table 8](#).

Table 8: Best overall response when confirmation of CR and PR required

Overall response First time point	Overall response Subsequent time point	BEST overall response
CR	CR	CR
CR	PR	SD, PD or PR*
CR	SD	SD provided minimum criteria for SD duration met, otherwise PD
CR	PD	SD provided minimum criteria for SD duration met, otherwise PD
CR	NE	SD provided minimum criteria for SD duration met, otherwise NE
PR	CR	PR
PR	PR	PR
PR	SD	SD
PR	PD	SD provided minimum criteria for SD duration met, otherwise PD
PR	NE	SD provided minimum criteria for SD duration met, otherwise NE
NE	NE	NE

CR=complete response; PR=partial response; SD=stable disease; PD=progressive disease; NE=nonevaluable

* If CR is truly met at first time point, then any disease seen at a subsequent time point, even disease meeting PR criteria relative to baseline, makes the disease PD at that point (since disease must have reappeared after CR). Best response would depend on whether minimum duration for SD was met. However, sometimes 'CR' may be claimed when subsequent scans suggest small lesions were likely still present and in fact the patient had PR, not CR, at the first time point. Under these circumstances, the original CR should be changed to PR and the best response is PR.

8.2.4 Confirmatory Measurement/Duration of Response

8.2.4.1 Confirmation

To be assigned a status of PR or CR, changes in tumor measurements must be confirmed by repeat assessments that should be performed at 4 weeks but no later than 5 weeks for patients in dose levels 1-4 (0.15 mg/kg, 0.3 mg/kg, 0.6 mg/kg, 1.2 mg/kg) in Part A after the criteria for response are first met. Response will be confirmed after 4 weeks or at the next scheduled scan (at Week 6 of the following cycle) for patients in dose level 5 (1.6 mg/kg) in Part A and all patients in Part B. If a confirmative scan is done after 4 weeks, the next scheduled scan (at Week 6 of the following cycle) may be omitted. In the case of SD, follow-up measurements must have met the SD criteria at least once after study entry at a minimum interval of 5 weeks.

8.2.4.2 Duration of Overall Response

The duration of overall response is measured from the time measurement criteria are met for CR or PR (whichever is first recorded) until the first date that recurrent or progressive disease is objectively documented (taking as reference for PD the smallest measurements recorded since the treatment started).

The duration of overall CR is measured from the time measurement criteria are first met for CR until the first date that recurrent disease is objectively documented.

8.2.4.3 Duration of Stable Disease

SD is measured from the start of the treatment until the criteria for progression are met, taking as reference the smallest measurements recorded since the treatment started.

8.3 Pharmacokinetics

Plasma concentrations of NDT-05-1040 will be measured from blood samples collected at the following timepoints for Part A:

- Cycle 1, Day 1:
 - Before SOI,
 - During the infusion: 20 m ± 5 m after the start of the last infusion step implemented at 6 mL/min rate
 - EOI; after EOI: 0.5 hr (±5m), 2 hr (±10m), 6 hr (±15m), 24 hr (±1hr), 48 hr (±2hr), 72 hr (±3hr)
- Cycle 1, Day 8: pre-dose
- Cycle 1, Day 22:
 - Before SOI
 - During the infusion: 20 m ± 5 m after the start of the last infusion step implemented at 6 mL/min rate
 - EOI; after EOI: 0.5 hr (±5m), 2 hr (±10m), 6 hr (±15m), 24 hr (±1hr), 48 hr (±2hr), 72 hr (±3hr)
- Cycle 2, Day 1: pre-dose

Plasma concentrations of NDT-05-1040 will be measured from blood samples collected at the following timepoints for Part B. (Note: timepoints are the same as the Part A PK sample collection with the exception of the 48 and 72 hr timepoint collections, which will not be measured in Part B):

- Cycle 1, Day 1:
 - Before SOI,
 - During the infusion: 20 m ± 5 m after the start of the last infusion step implemented at 6 mL/min rate
 - EOI; after EOI: 0.5 hr (±5m), 2 hr (±10m), 6 hr (±15m), 24 hr (±1hr)

- Cycle 1, Day 8: pre-dose
- Cycle 1, Day 22:
 - Before SOI
 - During the infusion: 20 m ± 5 m after the start of the last infusion step implemented at 6 mL/min rate
 - EOI; after EOI: 0.5 hr (±5m), 2 hr (±10m), 6 hr (±15m), 24 hr (±1hr)
- Cycle 2, Day 1: pre-dose

8.4 Anti-Drug Antibodies (ADAs)

Blood samples will be collected at the following timepoints for possible evaluation for ADAs:

- Cycle 1, Day 1: pre-dose
- Cycle 1, Day 15: pre-dose
- Cycle 2, Cycle 4, Cycle 6, Cycle 8, etc. (i.e., every even numbered cycle), up to one year: Day 1 pre-dose
- Year 2 and beyond: every 6 months
- EOT
- 30-Day Follow-up Visit after Last Dose

8.5 KRAS Genotyping

Depending upon availability and patient consent, we may request archival tumor sample and/or results of genomic tumor profile, but these are not required to confirm patient eligibility for dose levels 1-4 (0.15 mg/kg, 0.3 mg/kg, 0.6 mg/kg, 1.2 mg/kg) in Part A.

Confirmation of KRAS mutation is a requirement for dose level 5 (1.6 mg/kg) in Part A and for all patients in Part B. Genomic tumor profile results can be used. Otherwise, a tumor tissue sample (archival or fresh) can be tested locally for eligibility. Fresh biopsy (if needed) may be obtained only if it has minimal risk of complications for the patient. If such type of biopsy is needed but cannot feasibly be collected, the sponsor and Medical Monitor should be consulted.

Liquid biopsy may also be used to confirm KRAS status. In the case that both a liquid and tumor biopsy is available, the following criteria will be used to evaluate eligibility:

		Tumor	
		Wildtype	Mutant
Liquid	Wildtype	Fails Inclusion # 1	Meets Inclusion # 1
	Mutant	Meets Inclusion # 1	Meets Inclusion # 1

8.6 Immune Activation Biomarkers

Cytokines:

Blood samples will be collected during Cycle 1 (Week 1) for all patients in Part A of the study for determination of cytokines (IFN- γ , IL-1 β , IL-6, TNF- α):

- Pre-dose
- 10 \pm 3 minutes after SOI
- 60 \pm 10 minutes after EOI
- 6 hr \pm 15 minutes after EOI
- 24 hr \pm 1 hr after EOI

Dose levels 3 (0.6 mg/kg) and 4 (1.2 mg/kg) did not result in immune activation in Part A and therefore, cytokine activity will not be monitored at those two dose levels in Part B. However, if a patient, during or after any infusion of NBF-006, develops IRR symptoms (e.g., backache, fever, nausea, headache, rash, rapid heartbeat, low blood pressure, or trouble breathing), best attempts should be made to collect cytokines as described for Part A with the exception of 10 \pm 3 minutes after SOI, which should be collected as close as feasible to the IRR.

If there is no meaningful cytokine induction in the 6-patient dose level 5 (1.6 mg/kg) during Part A, then cytokine testing will also not be needed in the remaining 4 patients in Part B at that same dose level (1.6 mg/kg), unless there are symptoms of IRR.

Complement:

Blood samples will be collected during Cycle 1 (Week 1) for all patients in Part A and Part B of the study for determination of complement (CH50, Bb, C3a, C5a):

- Pre-dose
- 10 \pm 3 minutes after SOI
- 60 \pm 10 minutes after EOI
- 6 hr \pm 15 minutes after EOI
- 24 hr \pm 1 hour after EOI

8.7 Exploratory Biomarkers

Blood sample will be collected at baseline. PBMCs will be isolated from patient blood samples for exploratory studies. Tumor tissue (archival samples or those procured for routine medical care during the course of the study) may be retained from all patients in Parts A and B, for biomarker testing. Biomarkers may include (but are not limited to) GSTP or related proteins of the GST family.

8.8 GSTP Knockdown

Blood samples will be collected at the following timepoints for evaluation of GSTP KD in the 6 patients from Part A at 1.6 mg/kg dose level and from all patients in Part B of the study:

- Cycle 1, Day 1:
 - Before SOI
 - After EOI: 6 hr (± 15 m), 24 hr (± 1 hr)
- Cycle 1, Day 8: before SOI

Patients who are willing to provide exploratory pre- and on-study biopsies will be sampled prior to the first dose and 24 hours after the 4th dose in cycle 1, if clinically feasible. If possible, lesions selected as RECIST target lesions should not be biopsied.

8.9 GSTT1 Genotyping

In Part A dose level 5 (1.6 mg/kg) of the study, patients will not be stratified for the GSTT1-null genotype, but whole blood samples will still be collected during the screening visit and batch analyzed at a central lab.

Patients in Part B of the study will be stratified across all cohorts for the GSTT1-null genotype to ensure that all dose levels receive even distribution of GSTT1-null patients. Analysis will be done at a central lab from blood samples collected during the screening visit.

9.0 STATISTICS

Demographic data and disease-related characteristics will be summarized using descriptive statistics (count and percent, mean, median, standard deviation, minimum, maximum). All patient data, efficacy and safety data will be summarized. Results from Part A and Part B will be presented separately.

9.1 Analysis Populations

The Intent-to-Treat population will include all participants who were enrolled (signed consent) into the study, irrespective of whether study medication was administered or not.

Safety Evaluable Population: All patients who received any component of study treatment.

Efficacy Evaluable Population: Patients with measurable disease by RECIST 1.1 who had a baseline assessment and at least one post-baseline assessment. Responses must be confirmed at a second imaging evaluation that should be performed at 4 weeks but no later than 5 weeks for patients in dose levels 1-4 (0.15 mg/kg, 0.3 mg/kg, 0.6 mg/kg, 1.2 mg/kg) in Part A after response criteria are met. Response will be confirmed after 4 weeks or at the next scheduled scan (at Week 6 of the following cycle) for patients in dose level 5 (1.6 mg/kg) in Part A and all patients in Part B. If a confirmative scan is done after 4 weeks, the next scheduled scan (at Week 6 of the following cycle) may be omitted. Responders (PR and CR) with confirmatory imaging will be denoted as PR and CR. Those with only one evaluation documenting PR or CR will be denoted as partial response-unconfirmed (PR-UC) and complete response (CR-UC). The primary evaluation of efficacy will focus on PR and CR but analyses incorporating PR-UC and CR-UC will also be performed.

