Safety Evaluable Population: All patients who received any component of study treatment.

Efficacy Evaluable Population: Patients with measurable disease by RECIST 1.1 who had a baseline assessment and at least one post-baseline assessment. Responses must be confirmed at a second imaging evaluation that should be performed at 4 weeks but no later than 5 weeks for patients in dose levels 1-4 in Part A after the criteria for response are first met. Response will be confirmed at 4 weeks or at the next scheduled scan at Week 6 of the following cycle for patients in dose level 5 in Part A and all patients in Part B. If a confirmative scan is done after 4 weeks, the next scheduled scan may be omitted. Responders (partial response [PR] and complete response [CR]) with confirmatory imaging will be denoted as PR and CR, respectively. Those with only one evaluation documenting PR or CR will be denoted as partial response-unconfirmed (PR-UC) and complete response unconfirmed (CR-UC). The primary evaluation of efficacy will focus on PR and CR but analyses incorporating PR-UC and CR-UC will also be performed.

ABBREVIATIONS

ADA	anti-drug antibodies
AE	adverse event
Akt	protein kinase B
ALT/SGPT	alanine transaminase / serum glutamic-pyruvic transaminase
ANC	absolute neutrophil count
API	active pharmaceutical ingredient
AST/SGOT	aspartate transaminase / serum glutamic-oxaloacetic transaminase
AUC	area under the curve
CFR	Code of Federal Regulations
C _{max}	maximum concentration
CNS	central nervous system
CR	complete response
CT	computed tomography
CTCAE	Common Terminology Criteria for Adverse Events
dL	deciliter
DLT	dose-limiting toxicity
ECG	electrocardiogram
ECOG	Eastern Cooperative Oncology Group
eCRF	electronic case report form
EOI	end of infusion
EOT	end of treatment
ERK	extracellular signal-regulated kinase
FDA	Food and Drug Administration
GCP	Good Clinical Practice
GDP	guanosine diphosphate
GLP	Good Laboratory Practice
GST	glutathione S-transferase
GSTP	glutathione S-transferase pi
GTP	guanosine triphosphate
HED	human equivalent dose
HNSTD	highest non-severely toxic dose
hr	hour
IB	Investigator's Brochure
ICH	International Council for Harmonization
IEC	Independent Ethics Committee
IFN- γ	interferon-gamma
IL	interleukin
IL-1ra	interleukin-1 receptor antagonist
IND	Investigational New Drug (application)
IRB	Institutional Review Board
IRR	Infusion-related reaction
IV	intravenous
JNK	c-JUN N-terminal kinase
KD	knockdown

kg	kilogram
KRAS	Kirsten rat sarcoma

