7.3.1.6 Week 6 (Day 36-42)

- Tumor measurement (use same method as baseline) performed at the end of every even cycle for Part A dose levels 1-4 and performed at the end of every cycle for Part A dose level 5 and all patients in Part B.

7.3.2 Cycle 2

7.3.2.1 Week 1 (Day 1 should occur within 3 days of Day 42 of previous cycle)

- Physical Exam
- Weight

- Vital signs
- ECOG
- Hematology
- Blood chemistry
- Urinalysis
- Pregnancy test
- ADA assay sampling (pre-dose)
- PK blood sampling (pre-dose)
- NBF-006 administration
- Concomitant medications
- AEs

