9.3 Safety

Safety will be assessed by means of physical examination, weight, vital signs, performance status, laboratory evaluations (hematology, biochemistry), ECG, pain assessment and recording of concurrent illness/therapy and AEs. NCI CTCAE version 5.0 will be used to grade all toxicities. All related AEs will be monitored until resolution. Patients will be monitored for safety and concomitant medications throughout the study.

Safety data will be summarized for the safety evaluable population. These data will include AEs and laboratory parameters. AE terms will be coded using the most current version of MedDRA®.

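### The efficacy-evaluable set in section 9.1 requires a post-baseline assessment; if it is the Part B denominator, treated patients who are never scanned drop out, and a non-zero response or disease control percentage can only rise

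*Protocol*

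**What the plan says.** Section 9.1 of the protocol defines three sets.

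- **Intent-to-Treat:** "The Intent-to-Treat population will include all participants who were enrolled (signed consent) into the study, irrespective of whether study medication was administered or not". No analysis is assigned to it.
- **Safety Evaluable:** everyone who received any study treatment. Section 9.3 gives it a use: "Safety data will be summarized for the safety evaluable population".
- **Efficacy Evaluable:** "Patients with measurable disease by RECIST 1.1 who had a baseline assessment and at least one post-baseline assessment". The synopsis repeats this definition. The same paragraph sets the confirmation rules and closes with "The primary evaluation of efficacy will focus on PR and CR but analyses incorporating PR-UC and CR-UC will also be performed".

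Section 9.2.1 makes BOR a Part B primary endpoint. Section 9.4 adds DCR, the rate of SD, PR and CR together. Neither names a population. The synopsis presents results by dose cohort, and section 6.1.2 plans cohorts of 10, 10 and 4 in Part B.

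Tumor measurement is "performed at the end of every cycle for Part A dose level 5 and all patients in Part B", so the first scheduled Part B scan falls in Week 6. Section 7.4 adds a tumor measurement at end of treatment (EOT) for everyone who stops, and section 5.4.1 asks sites to make every effort to obtain those assessments. Section 5.4.2 replaces patients who discontinue or miss doses for reasons other than toxicity. It keeps replaced patients in the DLT assessment and is silent on efficacy.

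**The concern.** Membership of the efficacy set depends on something that happens after treatment starts: staying alive, well and in contact long enough to be assessed. Patients who die, deteriorate, refuse or are lost before any scan cannot be CR, PR or SD. Taking them out of the denominator therefore moves a non-zero percentage in one direction only.

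Part B has no control arm and small cohorts, so the percentage in each cohort is itself the result that readers will use. If one dose level loses more patients early than another, its percentage gains more, and the descriptive comparison of doses is blurred. Replacement adds to this: an early failure can be substituted by another patient, and the protocol does not say that the first patient still counts for efficacy.

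**Working it through.** **The plan's own figure.** The Part B size is a sum of cohorts: 10 + 10 + 4 = 24, as section 6.1.2 states. Section 9.6 says that no sample size calculation was done, so there is no power, response rate or dropout figure to reproduce.

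**Formula.** Let T be the number treated in a cohort, d the number with no post-baseline assessment, and x the number with the outcome (response or disease control). None of the d patients is among the x.

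- Rate in all treated patients: x/T
- Rate in the efficacy-evaluable set: x/(T − d)
- Ratio of the second to the first: T/(T − d), at least 1. If x = 0 or d = 0 there is no shift.

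The values of d and x below are assumptions; the protocol gives neither.

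**Case 1: losses are replaced (section 5.4.2, reasons other than toxicity).** I assume each replacement is assessed. The evaluable cohort then stays at 10 and T = 10 + d, so the factor is (10 + d)/10.

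| d | Factor | Evaluable set, x = 5 | All treated, x = 5 |
|---|---|---|---|
| 1 | 1.10 | 5/10 = 50% | 5/11 = 45% |
| 2 | 1.20 | 5/10 = 50% | 5/12 = 42% |
| 3 | 1.30 | 5/10 = 50% | 5/13 = 38% |

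Cohort of 4, d = 1: factor 5/4 = 1.25; 2/4 = 50% against 2/5 = 40%.

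**Case 2: losses are not replaced (toxicity).** T = 10 and the factor is 10/(10 − d).

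| d | Factor | Evaluable set, x = 5 | All treated, x = 5 |
|---|---|---|---|
| 1 | 1.11 | 5/9 = 56% | 5/10 = 50% |
| 2 | 1.25 | 5/8 = 63% | 5/10 = 50% |
| 3 | 1.43 | 5/7 = 71% | 5/10 = 50% |

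Cohort of 4, d = 1: factor 4/3 = 1.33; 2/3 = 67% against 2/4 = 50%.

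**Comparison of two doses.** Suppose two cohorts each show disease control in 5 of 10 evaluable patients, one with d = 0 and the other with d = 2 replaced. Both read 50% in the evaluable set. Among all treated they are 5/10 = 50% and 5/12 = 42%.

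**How likely is any loss?** If each patient has probability q of never being assessed, the chance of at least one among 10 is 1 − (1 − q)^10. For q = 5%, 10% and 30% this is 40%, 65% and 97%. This range for q is also an assumption.

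**Against sampling error.** The exact 95% interval for 5/10 is 18.7% to 81.3%. It contains every alternative shown for the cohort of 10, from 38% to 71%.

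**The case against.** The strongest objection is that the protocol never says that this set is the denominator. It defines three sets, one of which keeps the lost patients, and matching sets to endpoints is often left to the SAP. That is true, and a reader might wrongly infer that the protocol fixes the efficacy-evaluable set for BOR and DCR; it does not. What remains is a definition on the page. This is the only set with efficacy in its name, and its paragraph carries the statement on the primary evaluation. The alternatives fit poorly: Intent-to-Treat includes people who consented and were never treated, and the Safety Evaluable set is tied to safety data.

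A reader might also take 1.11, 1.25 and 1.43 as the general inflation. Section 5.4.2 does not support that. Its rule on losses other than toxicity is not limited to Part A, and most patients lost before a scan would fall under it, so the smaller factors are the usual case.

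It could be argued further that the response rules already cover such a patient, because Table 8 has a row in which two NE assessments give a best response of NE. This stands in part. The category exists, so calling the patient unclassifiable would be too strong. But section 8.2.3.4 starts from the premise that "It is assumed that at each protocol-specified time point, a response assessment occurs", and entries such as "SD provided minimum criteria for SD duration met, otherwise NE" work from recorded time points. No sentence places a patient who was never imaged.

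Four limits stand in full:

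- The EOT measurement makes d smaller.
- The counts of CR, PR and SD are the same under either denominator.
- The synopsis promises percentages only where meaningful, and DCR is the only endpoint called a rate.
- The word assessment is not qualified as a tumor assessment, so a looser reading would exclude fewer patients.

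**Conclusion.** The point holds as a cheap improvement. If the efficacy-evaluable set is used as its name suggests, the Part B response percentages and DCR are biased upward whenever a treated patient has no post-baseline assessment, and they are never biased downward. For 1 to 3 such patients in a cohort of 10 the factor is 1.10 to 1.30 where they are replaced and 1.11 to 1.43 where they are not. For one such patient in the cohort of 4 it is 1.25 or 1.33.

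This rests on three assumptions: that the set is the denominator, that d is above zero after EOT scans, and that replacements are themselves assessed. It would go too far to say that the bias undermines the trial's conclusions. All analyses are descriptive, no efficacy threshold or test is stated, and each shift lies within sampling error. The case for acting is that the error has a known direction, may differ between doses, and can be removed by wording.

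**What to change.** In section 9.1 and the synopsis:

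1. Name all treated patients with measurable disease at baseline as the primary denominator for BOR, DCR and any response percentage in each Part B dose cohort.
2. State that treated patients who are later replaced under section 5.4.2 remain in that denominator.
3. Count a patient with no post-baseline tumor assessment as NE, that is, a non-responder without disease control, and say that the assessment meant is a tumor assessment.
4. Keep the efficacy-evaluable analysis as supportive, and report the number of treated but unassessed patients in each cohort beside it.

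The cost is a few sentences. No extra patients, visits or data are needed. The downside is slightly lower reported rates.
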